7.3.19 Hepatitis serology

At screening (V1) and at visit V15 the following tests on hepatitis serology will be performed at the local laboratory:

- Hepatitis B screening to document the state of immunisation of past infection or active infection (HBsAg and HBsAb)
- Hepatitis C screening to document past or active infection with HCV RNA (quantitative)

All tests on hepatitis serology will be carried out on the same sample as collected for blood haematology/biochemistry.

7.3.20 Haematology/Biochemistry

All haematology/biochemistry will be performed in the local laboratory and will be assessed at each scheduled visit (V1 to V15 and at withdrawal visit when applicable) for the monitoring of transfusion requirements.

Complete blood count will be evaluated monthly.

Serum transaminases, bilirubin and alkaline phosphatase will be checked before the initiation of treatment, every 2 weeks during the first month and monthly thereafter.

Platelet count for checking exclusion criteria must be assessed between day -9 and day -7 of the screening period.

7.3.21 Ocular and audiometric test

Ocular examinations will be performed at baseline (V3 \pm 20 days) and at the end of treatment (V15 \pm 20 days).

An audiometric examination will be performed at V3 \pm 20 days and then at V15 \pm 20 days.

7.3.22 Pharmacokinetics

Samples collection for pharmacokinetics on V15 will consist of an additional 2ml blood each to allow for the assessment of steady state concentrations of DFP and DFX.

Whilst timing of dose and blood collection are not strictly defined throughout the study visits, patients are expected to take the last dose in the clinic, under supervision of qualified staff.

Blood sampling for pharmacokinetics (2 ml) for the assessment of peak drug concentrations should be collected within 4 hours after dosing according to the sparse sampling scheme specified in the SPM. It is critical that both sampling and dosing time are accurately recorded.

7.3.23 Adverse events

Information about all adverse events, whether volunteered by the subject, discovered by investigator questioning, or detected through physical examination, laboratory test or other means, will be collected and recorded on the Adverse Event CRF and followed as appropriate.

For details please refer to **section 16**.

7.3.24 Body height/weight

Auxological parameters such as weight and height will be evaluated at each monthly visit at V1 and from V3 to V15.

7.3.25 Pubertal staging

Pubertal stage measured according to Tanner staging system will be assessed at V3, V9 and V15.

7.3.26 Compliance

Compliance will be assessed at each visit from V4 to V15 by estimating DFP solution volume in each bottle or the number of DFX tablets in the blister pack remaining at each visit.

7.3.27 Quality of Life

QoL questionnaire will be assessed to evaluate the Health Related Quality of Life (HRQoL) from the point of view of parents or guardians of patients aged from 5 to less than 18 years through CHQ. CHQ will be filled in at V3, in V9 and at the end of treatment (V15) and scoring will be reported in the CRF.

7.3.28 Healthcare Resources

Healthcare resources as reported in **Section 4.4.6** will be assessed at each monthly visit from V4 to V15 and the following parameters will be recorded in the CRF: hospitalisation (ward, length of hospitalisation), outpatient visits (type of visit), tests performed outside those foreseen in the protocol.

8. CONCOMITANT MEDICATIONS

Regular medications needed to treat concomitant medical conditions may be continued during the study. Such concomitant medications must be recorded in the CRF. Patients must be instructed not to take any additional medications (including over-the counter-products) during the study without prior consultation with the investigator except those accepted by the investigator at screening. If concomitant therapy must be added or changed, the reason and name of the drug should be recorded on the CRF.

Due to the unknown mechanism of DFP-induced neutropenia, patients must not take medicinal products known to be associated with neutropenia or those that can cause agranulocytosis. Drugs reported to be associated with agranulocytosis include antimicrobial agents (chloranphenicol, penicillins, sulphonamides), analgesic/anti-inflammatory agents (aminopyrine, indomethacine, phenylbutazone), anticonvulsivants (phenytoin, carbamazepine), antithyroid agents (propylthiouracil), cardiovascular agents (hydralazine, procainamide, quinidine), hypoglycaemic agents (chlorpropamide), sedative (chlorpromazine, phenothiazines).

For any drug interaction concern with DFX, please refer to section 4.5 (Interaction with other medicinal products and other forms of interaction) of the DFX SmPC (Annex 1).

Potential drug interactions

Data indicate that DFP and DFX are primarily metabolised by UGT enzymes. Medications that are strong inhibitors or inducers of human UGT (e.g. rifampicin, carbamazepine, phenytoin, phenobarbital, ritonavir) will be prohibited during the study treatment.

Permitted Medications

All concomitant medications taken during the study will be recorded in the CRF. The minimum requirement is that drug name, dose administered and the dates of administration are to be recorded.

Prohibited Medications

CONFIDENTIAL

DEEP Consortium
DEEP2-Efficacy/Safety Study Protocol

Protocol No. DEEP-2

Subjects must abstain from taking known drugs that interfere with chelation. Patients and/or their parents/legal guardians must be instructed to use aluminium-containing therapies only after consultation with the investigator.

Non-Drug Therapies

Subjects should abstain from taking any non-prescription medication, vitamins, herbal and dietary supplements within 7 days (or 14 days if the drug is a potential enzyme inducer) or 5 half-lives (whichever is longer) prior to the first dose of study drug (Day 0) until completion of the follow-up visit (V16, month 13), unless in the opinion of the Investigator and Sponsor the medication will not interfere with the study.

9. INTERRUPTION OF TREATMENT

This section deals with a patient's premature withdrawal from the study before completing all scheduled visits. An individual subject may be withdrawn at the discretion of the responsible investigator and the study team for the reasons listed hereby. In the event one or more subjects are withdrawn, additional subjects may be enrolled to ensure an adequate number of subjects complete the cohort.

Reasons that a patient must discontinue participation in a clinical study are considered to constitute one of the following:

1. unsatisfactory therapeutic effect (quarterly increase in ferritin levels of at least 1500 ng/ml as detected by two determinations performed at no more than two weeks interval, or if cardiac MRI T2* decreases under 10ms)
2. subject's condition no longer requires study treatment
3. DFX treatment at 10 mg/kg/day (for safety reasons) for more than 4 weeks
4. DFP or DFX administration suspended (for safety reasons) for more than 4 weeks
5. adverse event(s) requiring change of chelation therapy, including moderate or severe Neutropenia
6. significant protocol violation
7. subject/legal guardian withdrew consent/assent
8. lost to follow-up
9. administrative problems
10. death

In the absence of a medical contraindication or significant protocol violation, the investigator may make an effort to keep the subject in the study. Should a subject withdraw or be withdrawn by the legal guardian, he/she has to complete a full set of the 'end-of-study phase assessments', i.e. a full V16 evaluation. Relevant records will have to be done on the corresponding CRF pages.

This requirement does not refer to patients who passed the screening and washout period and were found not to be eligible for treatment.

Patients prematurely withdrawn from the treatment will be considered treatment failures.

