4.3.1 Definition of successful chelation

The following criteria will be used to identify a treatment success:

- Criterion A - Serum Ferritin Levels:** success for patients with baseline serum ferritin levels of 2500 ng/mL or more will be defined as a 20% reduction or more after 1 year treatment. Success for patients with baseline serum ferritin levels less than 2500 ng/mL will be defined as any decrease in serum ferritin, or an increase in serum ferritin, if that increase is less than or equal to 15% of the baseline level, as long as the increase does not result in a serum ferritin above 2500 ng/mL within 12 months despite continual transfusional therapy.
- Criterion B - MRI T2* Cardiac Iron Concentration:** success for patients with baseline values of 20 ms or more will be defined as any increase in T2* or, if there is a decrease, the decline is not more than 10% after 1 year, as long as this does not result in a value below 20 ms. Success in patients with a baseline less than 20 ms will be defined as an increase in T2* of 10% or more despite transfusional therapy.

Table 1 summarises the applied criteria.

Table 1. Definition of treatment success

Baseline ferritin \geq 2500 ng/mL	Reduction of 20% or more after 1 year treatment
Baseline ferritin $<$ 2500 ng/mL	
 any decrease increase \leq 15% as long as the increase doesn't result in ferritin $>$ 2500 ng/ml after 1 year treatment
Baseline MRI T2* $<$ 20 ms	
 Increase of 10% or more after 1 year treatment
Baseline MRI T2* \geq 20 ms	
 any increase decrease \leq 10% after 1 year treatment as long as the decrease does not result in MRI T2* value $<$ 20 ms

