6.3 Dose Adjustments

Dose adjustments for both DFP and DFX will be allowed for efficacy reasons (scaling up) or for safety reasons including the presence of markers indicative of over-chelation (scaling down).

DFP can be scaled up in steps of 12.5 mg/kg/day (to a maximum daily dose of 100 mg/kg) according to the individual patient's response defined as an increase of serum ferritin levels > 20% compared to the previous determination.

DFX will be scaled up in steps of 5 to 10 mg/kg (to a maximum daily dose of 40 mg/kg) according to the individual patient's response defined as an increase of ferritin levels > 20% compared to the previous determination.

For patients with a stable serum ferritin value >1500 (no increase or any increase <20%) and not showing a downtrend over a 3-month-period , DFP or DFX can be also increased.

DFP and DFX must be scaled down for the safety reasons detailed in **Table 4**.

Table 4. Scale down adjustment for DFP and DFX (safety reasons)

Serum creatinine increased by >33% from baseline OR Reduction in creatinine clearance (estimated with the Schwartz formula) ≤ 90ml/min and >60 ml/min in two consecutive measurements	No dose adjustment.	Reduce DFX in steps of 10 mg/kg/day until value returns to baseline value and continue DFX with the adjusted dose for 1 month. If the increase persists interrupt DFX. If after DFX interruption value returns to baseline value or > 90 ml/min for creatinine clearance restart DFX at 50% of the last dose and then escalate by 10 mg/kg/day at 1 month intervals provided that value increase does not recur. Monitor serum creatinine, creatinine clearance and urine protein/creatinine ratio weekly (+/- 7 days) during the period of abnormal value and during the first month after dose modification, then monthly.
Urine protein/creatinine ratio ≥ 0.5 in two consecutive measurements	No dose adjustment.	Reduce DFX in steps of 10 mg/kg/day until value returns to < 0.5. If the increase persists interrupt DFX. After the ratio improves, restart DFX at 50% of the last dose and then escalate by 10 mg/kg/day at 1 month intervals provided that value increase does not recur. Monitor serum creatinine, creatinine clearance and urine protein/creatinine ratio weekly (+/- 7 days) during the period of abnormal value and during the first month after dose modification, then monthly.

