7.3.12 Serum Ferritin

All the determinations relative to serum ferritin will be carried out on the same sample collection as haematology/biochemistry at screening, and at each monthly visits for evaluation at the local laboratory for patient clinical monitoring.

Additional serum ferritin determinations will be performed in blood collected in separate vials at V3, V6, V9, V12, V15 and will be evaluated in the centralised laboratory/ies as specified in the SPM. Central determination of ferritin will be performed also in case of withdrawal during the early termination visit. Central determinations will be used for formal analyses.

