11.12 Sample Size and power considerations

Primary efficacy objective

Assuming type I and type II errors of 0.025 and 0.20, respectively, and a one-sided test, and under the assumptions that the expected proportion of subjects declared treatment successes in the DFX arm is 65%, and the expected proportion of subjects declared treatment successes in the DFP arm is 67.5% a sample size of 310 subjects, randomized in a 1:1 ratio to DFP or DPX will yield 80% power to demonstrate non-inferiority of DFP versus DFX. Taking into account a possible dropout rate of about 20% a total enrolment of 388 patients aged from 1 month to less than 18 years are expected to be included in the trial.

Secondary efficacy objective

Sample size requirements for the secondary efficacy objectives (non-inferiority in terms of ferritin levels and cardiac MRI T2*) are provided in the following.

Based on published literature, testing for non-inferiority is appropriate also when comparing DFP to DFX efficacy in terms of serum ferritin levels. In this case, considering a hypothesis testing on the continuous measure, a non inferiority margin of 400 ng/ml is considered a reliable estimate of the true allowed maximum difference between the IMPs in order to assume DFP to be non-inferior to DFX in controlling iron overload in patients affected by hereditary haemoglobinopathies. The standard deviation of the differences is available by pooling findings from paediatric studies conducted in Europe and outside (El Alfay M et al., 2010), and a reliable and conservative estimate can be 1000 ng/mL.

On these assumptions, 310 evaluable patients are sufficient to provide at least 90% power to demonstrate non inferiority of DFP to DFX, assuming a type I error of 0.025 and a one-sided test.

When considering efficacy in terms of cardiac MRI T2*, less reliable estimates of treatment efficacy are available, especially in the paediatric population. However, there are no reasons for not assuming at least a non inferiority of DFP to DFX, considering also the known beneficial effects of DFP at the cardiac level. Based on the limited published figures of cardiac MRI T2* in the paediatric population and taking into account adult data, some plausible scenarios of sample sizes and related powers are provided in the following **Table 7**, assuming a type I error of 0.025 and a one-sided test. Detailed power curves will be provided in the statistical plan.

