11.13 Handling of missing data

A negligible amount of missing data is expected in this study because the patient population under study (patients affected by haemoglobinopathies requiring chronic transfusion and chelation therapy), and their parents, are accustomed to routine close monitoring in clinical visits, are used to frequent lab tests and comply with uncomfortable examinations (MRI), and are generally willing to participate in trials that may lead to increasing the availability of treatments. Moreover, the estimated treatment effect is not expected to be importantly biased in favour of the experimental treatment due both to the choice of the comparator and of the primary endpoint.

DFX is an oral chelator as DFP, and its compliance is expected to be comparable to that of DFP, or even better taking into account the once a day administration.

The completeness of the data that will allow the estimate of the primary endpoint (percentage of successfully chelated patients) is expected to be high due to the type of patients and condition.

Finally, patients who prematurely discontinue the trial for any reason will be considered treatment failures.

Assuming the worst scenario for incomplete data in order to provide conservative estimates for the trial results, the imputation of missing data will only apply to missing data because of a missing visit. This will affect the trend analysis for the secondary evaluation on serum ferritin levels. In this case, Linear Mixed Models (LMM) will be used as imputation method for missing data.

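### Every withdrawal is scored as a treatment failure, and only the DFX arm has a rule that forces withdrawal after a low-ferritin dose reduction

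*Combined protocol and SAP*

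**What the plan says.** **Scoring of withdrawals.** Section 9 lists the reasons for which a patient must discontinue and closes with "Patients prematurely withdrawn from the treatment will be considered treatment failures". Section 11.13 adds that "patients who prematurely discontinue the trial for any reason will be considered treatment failures". Three reasons matter here:
- Reason 2: "subject's condition no longer requires study treatment". It names no ferritin value.
- Reason 3: DFX at 10 mg/kg/day, for safety reasons, for more than 4 weeks. No such reason is listed for DFP.
- Reason 4: either drug suspended, for safety reasons, for more than 4 weeks.

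**Low ferritin.** Section 6.3 counts markers of over-chelation among the safety reasons for scaling down. At ferritin of 500 ng/mL or less, Table 4 halves the dose in both arms. If ferritin is still below 500 at the next monthly check, either drug may go on after consultation with the Coordinating Investigator. The DFX cell then speaks of restarting the drug, although it has ordered only a reduction.

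**Success.** Under criterion A (Section 4.3.1), success from a baseline below 2500 ng/mL "will be defined as any decrease in serum ferritin", or a limited rise, judged after 1 year. Patients aged 10 or over who can be scanned without sedation must also meet criterion B on cardiac T2*.

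**Analysis sets.** PP1 is primary and requires the composite at baseline and at 1 year (Sections 11.2 and 11.6). ITT supports the non-inferiority result and is the set for the superiority test.

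**Data at withdrawal.** Section 7.3.12: "Central determination of ferritin will be performed also in case of withdrawal during the early termination visit".

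**The concern.** The failure rule does not separate a patient who leaves because ferritin has fallen far from one who leaves because the drug did not work (reason 1) or was not tolerated (reason 5). Taken alone, that is a blunt but common convention. The difficulty is that the rules feeding it differ by arm.

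Take a chelation-naive child under 10 with baseline ferritin of 1000 ng/mL that falls to 400.
- On DFX at 20 mg/kg, Table 4 halves the dose to 10 mg/kg/day and would allow continuation. Reason 3 requires withdrawal once more than 4 weeks have passed at that dose. The child is a failure in ITT and is absent from PP1.
- On DFP, the dose is also halved, but no rule forces withdrawal. The child can reach month 12 and be scored by criterion A.

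The same ferritin response can thus be a failure in one arm and a success in the other. A rule that lowers only the DFX success rate favours DFP, and it does so in the ITT analysis on which superiority is tested.

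**Working it through.** **1. The plan's own sample size.** Inputs from Sections 11.1 and 11.12: "type I and type II errors of 0.025 and 0.20, respectively, and a one-sided test"; success 65% on DFX and 67.5% on DFP; margin 12.5 points.

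n per arm = (1.960 + 0.842)² × (0.65×0.35 + 0.675×0.325) / (0.125 + 0.025)² = 7.849 × 0.446875 / 0.0225 = 155.9, so 156 per arm or 312 in total. The plan states 310, which gives 79.8% power. With 20% dropout, 310/0.80 = 387.5, so 388, as stated. The planned size is sound and does not depend on this rule.

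**2. The low-ferritin route.**
- Section 6.2 and Table 3: DFX starts at 20 mg/kg in naive and prior-DFP patients, and at not less than 20 mg/kg after DFO.
- Table 4: 50% of 20 = 10 mg/kg/day.
- Section 7.1: local ferritin is checked monthly, so a patient still below 500 at the next check has been at 10 mg/kg/day for about a month, and reason 3 is then at or near its 4-week limit.
- A patient on 30 mg/kg would be halved to 15 mg/kg/day, which reason 3 does not name. The route therefore concerns patients on 20 mg/kg.
- Section 5.1: naive patients may enter from 800 ng/mL, so falls to 500 or less are plausible.

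**3. Effect in ITT.** The Wald interval of Section 11.6 is used with 194 per arm. The plan gives no rate of such withdrawals, so the shares below are assumptions. Each share is the part of an arm moved from success to failure.

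One patient: 1/194 = 0.52 points. A net excess of five: 5/194 = 2.58 points, which is 2.58/12.5 = 21% of the margin and about the assumed 2.5-point advantage of DFP.

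*False superiority*, true rates 65% in both arms, loss in DFX only: Φ(d/SE − 1.96), where d is the induced difference.
- 2%: SE = √[(0.63×0.37 + 0.65×0.35)/194] = 0.0487; Φ(0.41 − 1.96) = 6.1%.
- 5%: SE = √[(0.60×0.40 + 0.65×0.35)/194] = 0.0491; Φ(1.02 − 1.96) = 17.3%.
- No loss: 2.5%.

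These figures ignore the preceding PP1 non-inferiority step, which can only lower them.

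*False non-inferiority in ITT*, DFP truly 12.5 points worse (52.5% v 65%), loss in DFX only: Φ((0.525 − p_DFX + 0.125)/SE − 1.96).
- 2%: Φ(0.02/0.0499 − 1.96) = 6.0%.
- 5%: Φ(0.05/0.0502 − 1.96) = 16.7%.

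*Other patterns at the planned rates:*

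| Loss in DFX | Loss in DFP | Difference (points) | ITT non-inferiority power |
|---|---|---|---|
| 0% | 0% | +2.5 | 87.8% |
| 5% | 5% | +2.5 | 85.8% |
| 5% | 0% | +7.5 | 98.4% |
| 0% | 5% | −2.5 | 53.6% |

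**4. Effect in PP1.** PP1 omits these patients rather than failing them. If 5% of the DFX arm would have been successes and is removed, the DFX rate becomes 0.60/0.95 = 63.2%. That is a shift of 1.8 points against 5 points in ITT.

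**The case against.** The strongest defence is that Table 4 already deals with low ferritin by reduction and continuation, and that Section 9 encourages investigators to keep patients in the study. Failure scoring is prespecified, is worded the same for both arms, and is a recognised conservative convention. No rate is given, and equal losses do not move the difference. All of this stands, except that equal wording does not give equal effect when reason 3 exists for one drug only.

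Several stronger readings are tempting, and the documents do not support them.
- *That over-chelation leads to a hold of more than 4 weeks under reason 4.* Table 4 orders no hold at low ferritin. The word for restarting in the DFX cell is an inconsistency, not a suspension rule.
- *That reason 2 describes the best responders.* It names no ferritin value and could equally cover a change in the underlying disease or in the need for transfusion.
- *That the rule turns an observed success into a failure.* Criterion A is judged after 1 year. With transfusions continuing, a ferritin at withdrawal is not the 1-year outcome, and older patients must also meet criterion B.
- *That the primary analysis scores these patients as failures.* By definition PP1 leaves out all patients without a 1-year composite.

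A fair objection to any remedy is that the trial is open label, so scoring by the recorded reason alone would let an unblinded judgement decide the outcome. The remedy therefore needs an objective trigger.

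**Conclusion.** The point holds in a limited form. Sections 9 and 11.13 make no exception for withdrawals due to reason 2 or to low ferritin. Reason 3, read with Section 6.3 and Table 4, gives a documented route by which strong ferritin responders on DFX, but not on DFP, become ITT failures. The resulting bias from that route runs toward DFP, in the ITT support for non-inferiority and in the ITT superiority test. Reasons 2 and 4 apply to both arms, and a loss confined to DFP would work against it.

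The size is 0.52 points per patient. A loss of 2% to 5% in DFX alone (about 4 to 10 of 194) would raise false superiority from 2.5% to about 6% to 17%. These shares are assumptions, as is the premise that every such patient would have been a success at month 12. A reader might infer that the trial's primary conclusion is compromised. The documents do not show that: PP1 is primary, its shift is smaller, and the number affected may be low. No stated sample-size figure is wrong. The contradiction between Table 4 and reason 3 needs resolving whatever the number turns out to be.

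**What to change.** 1. Reconcile the low-ferritin row of Table 4 with reasons 3 and 4 of Section 9, including the restart wording in the DFX cell. This review takes no view on which clinical rule is right.
2. In the ITT analysis, take patients withdrawn under reason 2, 3 or 4 whose central ferritin at withdrawal is at or below the Table 4 low-ferritin value. Classify them by criterion A on that sample against baseline. Where criterion B applies, use the latest on-treatment T2*, and score failure if there is none. All other withdrawals stay failures.
3. Leave the PP1 definition unchanged. Report withdrawals by reason and arm, and give the all-failure rule as a sensitivity analysis.

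The cost is wording in Sections 9, 11.6 and 11.13 and a withdrawal-reason code. No extra sample is needed, because the central ferritin at withdrawal is already planned. The drawback is that these few patients are classified before month 12 in an open-label trial, which the central-ferritin trigger limits. The withdrawal visit includes no MRI, so patients who need criterion B and leave before the month 6 scan would normally remain failures. So would a patient whose ferritin has risen above the threshold by the withdrawal visit.
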